### 3. Third visit: ("1 week followup")

Third visit is an approximately 1 week post-surgical follow-up and is standard of care. This visit will require approximately 15 – 30 minutes. Should any complication be observed at this time, appropriate standard of care interventions will be made.

### 4. Fourth visit: ("8 week: crown impression")

This visit is an approximately 8 week post-surgical followup and is standard of care. At this visit, the implant health and osseointegration assessed by tactile evaluation and impressions will be taken for a final crown. At this visit, a 3D intraoral scan will be performed for research purposes. This visit will require approximately 1.5 hours. Should any complication be observed at this time, appropriate standard of care interventions will be made. If the implant has failed to integrate, the implant will be removed (this is atraumatic and without discomfort) and the patient will be referred to the UIC college of dentistry dental clinics or their dentist for further treatment or retreatment and the subject may be discontinued from the study.

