## Study Outcomes:

- Primary outcomes will be volume of the alveolar ridge at 12 months as measured by 3D intraoral scanning.
- Secondary outcomes will be implant survival, bleeding upon probing, marginal bone levels (MBLs) as measured by peri-apical radiographs and patient satisfaction as measures by the OHIP patient survey.

The research study will be performed at the UIC Dental School Clinical Research Center and will involve multiple clinic visits. These clinic visits usually occur at the same time as the subjects clinic visits for implant therapy, to avoid any research-only visits. The schedule for obtaining a dental implant is shown above in Figure 1 in blue with research visits shown in green and is described below:

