### 1. First visit: ("Screening/Enrollment")

Subject screening, enrollment and the informed consent discussion will occur at this visit. Upon obtaining consent, medical and dental history may also be obtained from subjects. A scanned image of the subjects jaw bones, called a "cone beam CT" (CBCT) in addition to a 3D intraoral scan, will be obtained for the purpose of standard of care. This visit will require 30 - 60 minutes.

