### 6. Sixth visit: ("1 year follow-up")

This final visit will be approximately 1 year post-surgical followup and is performed in accordance with standard of care. Additionally, a 3D intraoral scan will be performed, subject will be asked to complete the OHIP patient satisfaction questionnaire and will receive a \$50 gift card for research purposes.

This visit will require approximately 30 – 60 minutes. Should any complication be observed at this time, appropriate standard of care interventions will be made at that time and the subject will be referred to the UIC College of Dentistry dental clinics or their dentist for further treatment or retreatment.

All 3D intraoral scans are light-based, are not x-ray scans, and utilize scanners sold to and used by dentists in replacement of conventional impressions

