## **9.0 Data Analysis**

Data analysis will be performed by the UIC PI in collaboration with the Co-I's using SPSS, SAS or similar software. A biostatistician may be consulted for statistical analysis, if required. Data will be de-identified prior to release to any statistician not listed as study personnel on Appendix P.

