There are a number of expected adverse events related to implant with crown surgery, including bleeding and bruising after surgery, post-surgical pain, infection, delayed healing, temporary speech problems, bone fracture, temporary or permanent damage to the nerves of the jaw, loss of bone on the upper or lower jaw (including altered appearance of the gum line), infection in the bone, damage to the adjacent teeth, chronic pain, abscess, and infection of the gums which may be unrelated to the study intervention (allograft).

A risk of implant treatment is failure of the implant prior to restoration or 'early' failure due to the lack of Osseointegration. This is associated with no pain or infection and the implant can be easily removed. Following 8 weeks of healing of the site, an implant can be replaced. In this study, if an implant is lost in the patient receiving the gum graft, the gum graft would not be removed.

Adverse events related to the PerioDerm® allograft include local or systemic infection, dehiscence (*wound rupture along incision line*) and/or necrosis (*death of tissue*) due to poor revascularization and allergic response to component(s) of the graft.

The UIC subject's treating clinician, who may or may not be a member of the research team, will attend to these adverse events until they have resolved and/or will refer the UIC subject to the appropriate provider as needed. These anticipated adverse events are described in the informed consent document and will be recorded on the appropriate CRF. Implant failure will result in dismissal of the subject and appropriate referral to the local dentist or UIC College of Dentistry clinics for further treatment.

Serious adverse events that are both unexpected and considered to be related to the study intervention will be reported to the UIC IRB in accordance with UICOPRS reporting guidelines. Anticipated adverse events that are not serious but occur at a frequency or intensity greater than anticipated by current clinical practice knowledge will also be reported to the UICIRB in accordance with UICOPRS reporting guidelines.

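### The 8-week and screening scans have no stated role in the 12-month primary comparison; a prespecified repeated-measures model would use them, for a modest gain

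*Combined protocol and SAP*

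**What the plan says.** Section 6.0 schedules three intraoral scans.

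- **First visit (screening):** the scan is taken with the cone beam CT, "in addition to a 3D intraoral scan, will be obtained for the purpose of standard of care".
- **Fourth visit (8 weeks):** "At this visit, a 3D intraoral scan will be performed for research purposes".
- **Sixth visit (1 year):** "Additionally, a 3D intraoral scan will be performed, subject will be asked to complete the OHIP patient satisfaction questionnaire".

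Under Study Outcomes, the primary outcome is "volume of the alveolar ridge at 12 months as measured by 3D intraoral scanning". It does not mention change from baseline or the 8-week value. The secondary outcomes are implant survival, probing bleeding, radiographic bone level and the OHIP survey; none uses an intraoral scan. Section 11.2 lists 8 weeks among the data collection timepoints without giving the data a use.

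On analysis, Section 9.0 says "Data analysis will be performed by the UIC PI in collaboration with the Co-I's using SPSS, SAS or similar software". Neither Section 9.0 nor Section 12.0 gives a model, an analysis set or a rule for missing data.

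On leaving the study, the wordings differ. At the fourth and fifth visits (Section 6.0), discontinuation after failed integration is optional. Section 7.0 makes exclusion definite and adds site infection as a trigger. Section 11.2 says "Implant failure will result in dismissal of the subject".

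**The concern.** A scan done for research should have a stated purpose, and this one has none. The protocol also creates missing 12-month volumes, because subjects may or must leave after implant failure or site infection. Infection is a listed risk of the allograft (Section 7.0), so losses could differ between arms. The enrolment margin in Section 5.0, up to 60, is for screening failures and not for losses after randomisation. With 20 per group, two losses are 10% of an arm.

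If the 12-month volumes were simply compared among those who have them, a subject lost after week 8 would leave the primary comparison although a post-surgery volume exists. That wastes some information. If the subjects who leave differ in volume, and leave more often from one arm, it also biases the contrast.

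**Working it through.** **Inputs.** From the documents: 20 subjects per group (Section 12.0), with scans at screening, 8 weeks and 12 months (Section 6.0). The documents give no loss rate, no correlation between the 8-week and 12-month volumes, and no SD, alpha or power. The total of 40 therefore cannot be rederived; it is used here only as the arm size. My assumptions are a share d lost after the 8-week scan of 5% to 20%, a correlation rho of 0.3 to 0.9, and two-sided 0.05.

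**1. Precision, same random loss in both arms.** With n randomised and m = n(1 − d) seen at 12 months, the variance of an arm mean, in SD² units, is

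- 12-month values only: 1/m
- using the 8-week value as well: (1 − rho²)/m + rho²/n

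The ratio is 1 − rho² × d, so the reduction is rho² × d.

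- rho 0.7, d 10% (m = 18): 0.49 × 0.10 = 4.9%
- rho 0.7, d 20% (m = 16): 0.49 × 0.20 = 9.8%
- smallest: 0.09 × 0.05 = 0.45%
- largest: 0.81 × 0.20 = 16.2%

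This is a large-sample formula. With baseline volume in the model, rho is the correlation that remains after baseline adjustment.

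**2. What that means for power.** Twenty per arm gives 80% power for (1.960 + 0.842) × √(2/20) = 0.886 SD. At that effect and rho 0.7:

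| Lost after week 8 | 12-month values only | With the 8-week scan |
|---|---|---|
| 10% | 18.0 per arm, power 75.7% | 18/0.951 = 18.9 per arm, power 77.8% |
| 20% | 16.0 per arm, power 70.7% | 16/0.902 = 17.7 per arm, power 75.1% |

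If half of a 20% loss leaves no 8-week scan, 18 per arm have that scan and 16 of them have the 12-month scan. The effective number at rho 0.7 is then 16/(1 − 0.49 × 2/18) = 16.9 per arm (16.5 at rho 0.5, 17.6 at rho 0.9).

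**3. Bias, all loss in one arm, lowest 8-week volumes lost.** The two lowest of 20 normal values sum to −3.275 SD in expectation, and the four lowest to −5.33 SD. The upward shift in that arm's 12-month completers mean is

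- 2 lost: 3.275/18 × 0.7 = 0.127 SD (0.055 at rho 0.3, 0.164 at rho 0.9)
- 4 lost: 5.33/16 × 0.7 = 0.233 SD (0.100 at rho 0.3, 0.300 at rho 0.9)

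Regression on the 8-week value brings this to about 0. That result is built into the assumption, because here the 8-week volume alone decides who is lost.

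**4. Bias under other patterns.** Large-sample simulation, rho 0.7, bias in SD:

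| Loss in the two arms | Loss depends on | Completers | Repeated measures |
|---|---|---|---|
| 10% and 10% | 8-week volume | about 0 | about 0 |
| 5% and 15% | 8-week volume | 0.10 | 0.00 |
| 10% and 10% | 12-month volume | about 0 | about 0 |
| 5% and 15% | 12-month volume | 0.15 | 0.09 |
| 0% and 20% | 12-month volume | 0.32 | 0.19 |

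When loss depends on the unseen 12-month volume (missing not at random), the model removes only part of the bias. In the 5% and 15% case it leaves 0.14 SD at rho 0.3 and 0.04 SD at rho 0.9.

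**The case against.** The strongest reply is that the protocol states no analysis at all. A reader might infer that it prescribes a completers analysis. It does not: a 12-month endpoint is compatible with imputation or with a repeated-measures model. That stands, and the defect is the silence. With no missing-data rule, dropping subjects without a 12-month scan is one possible outcome, and nothing in the text rules it out.

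A reader might also infer that dismissed subjects contribute nothing to the trial. That is wrong. Implant survival is a secondary outcome, and a failed implant is an event in it. The gap concerns the primary comparison only.

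Third, a reader might infer that the 8-week scan corrects the bias from losses. The documents do not support this:

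- The stated triggers are failed integration, judged by touch, and infection. No section links dismissal to scanned volume.
- Failure can be found and the implant removed at the 8-week visit itself, and the text does not say whether the scan comes first. Earlier losses have no post-surgery scan.
- After removal, the model predicts a volume as if the implant had stayed, which is a hypothetical quantity.

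Finally, baseline adjustment is less simple than it looks. Section 4.0 admits patients whose tooth is still to be extracted, and the only pre-surgery scan described is at screening. For them it may show a ridge with the tooth in place.

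These limits stand and shrink the point. They do not remove it: the scan has no stated use, and in every pattern checked the model's bias was no larger than the completers' bias beyond simulation error.

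**Conclusion.** The point holds in a limited form. The 8-week and screening scans have no stated role in the primary comparison, and a subject without a 12-month scan has no value for it. A repeated-measures model is a better default because it uses scans already planned.

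The gain is modest. At rho 0.7 and 10% late loss, power at the reference effect rises by about two percentage points (75.7% to 77.8%), and by less when losses come before a usable 8-week scan. With no losses, the model gives essentially the same 12-month contrast as a baseline-adjusted analysis of that visit. The completers bias of 0.13 to 0.23 SD belongs to one deliberately one-sided pattern at rho 0.7 and is not a forecast for this trial. Every size quoted rests on assumed loss rates and correlations.

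This is a cheap improvement and not a flaw that threatens the trial. It should not be called free: it relies on missing at random, and it obliges the sponsor to state the estimand.

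**What to change.** In Section 9.0:

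1. Prespecify a mixed model for repeated measures of ridge volume at 8 weeks and 12 months, in all randomised subjects with a usable post-surgery scan, analysed in the arm to which they were randomised. Include arm, visit, arm by visit, and baseline volume with its interaction with visit. The primary contrast is the arm difference at 12 months; the 8-week difference is secondary.
2. State how implant failure is handled in the estimand, and whether a volume as if the implant had stayed is the quantity wanted.
3. Define the baseline scan for subjects whose tooth is extracted after screening.
4. Report by arm, with reasons, the subjects who have no post-surgery scan and those who have only the 8-week scan.
5. Add a missing-not-at-random sensitivity analysis, for example shifting the unobserved 12-month volumes in one arm by stepped amounts until the conclusion changes.

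Reconcile the discontinuation wordings in Section 6.0 (fourth and fifth visits), Section 7.0 and Section 11.2, since they decide who is missing at 12 months. The reconciled text should also say whether the 8-week scan precedes any implant removal at that visit.

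The cost is protocol text and some statistical time. No visit, scan or subject is added, and the software already named can fit the model.

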### 5. Fifth visit (10-12 week; crown delivery)

This visit is approximately 10-12 weeks post-surgery and is standard of care. At this visit, implant health and osseointegration will be assessed by tactile evaluation and the final crown will be placed. This visit will require approximately 1.5 hours. Should any complication be observed at this time, appropriate standard of care interventions will be made. If the implant has failed to integrate, the implant will be removed (this is atraumatic and without discomfort) and the patient will be referred to the UIC College of Dentistry dental clinics or their dentist for further treatment or retreatment and the subject may be discontinued from the study.

### 6. Sixth visit: ("1 year follow-up")

This final visit will be approximately 1 year post-surgical followup and is performed in accordance with standard of care. Additionally, a 3D intraoral scan will be performed, subject will be asked to complete the OHIP patient satisfaction questionnaire and will receive a \$50 gift card for research purposes.

This visit will require approximately 30 – 60 minutes. Should any complication be observed at this time, appropriate standard of care interventions will be made at that time and the subject will be referred to the UIC College of Dentistry dental clinics or their dentist for further treatment or retreatment.

All 3D intraoral scans are light-based, are not x-ray scans, and utilize scanners sold to and used by dentists in replacement of conventional impressions

## **7.0 Expected Risks/Benefits**

The risks of dental implant therapy are minimal but include complications such as bleeding and bruising after surgery, post-surgical pain, infection, delayed healing, temporary speech problems, bone fracture, temporary or permanent damage to the nerves of the jaw, loss of bone on the upper or lower jaw (including altered appearance of the gum line), infection in the bone, damage to the adjacent teeth, chronic pain, abscess, and infection of the gums.

Risks of a PerioDerm® allograft include local or systemic infection, dehiscence (*wound rupture along the line of incision*) and/or necrosis (*death of tissue*) due to poor revascularization or allergic response to some component(s) of the graft material.

In accordance with the graft manufacturer's instructions, tissue recipient records for subjects receiving PerioDerm® will be maintained for the purpose of post-transplant tracing. This may increase the risk to the privacy of subjects randomized to +Graft.

CBCT and other 3D intraoral scanner capture light-generated images which are compiled by the appropriate software into a 3 dimensional geometric image. Since these scanners does not utilize xray technology, the medical risks of use are minimal and include mild fatigue of the facial muscles.

Subjects will be encouraged to contact the PI in the event of medical emergencies related to his/her dental care and will be provided a 24-hour emergency contact number. Subjects experiencing complication may require additional (>5) clinic visits during the course of this study. This is clearly indicated within the consent document.

If implant integration fails or the implant site is infected, the implant will be removed or the site infection treated using standard dental therapies. The subject will be excluded from this study and referred to UIC College of Dentistry for care.

Restoration of the oral cavity is likely to benefit all subjects, irrespective of study group. The potential for an enhanced restoration in the +Graft study group, as compared to the -Graft group, is the focus of this study.

Results from this research may lead to modifications in standards of care which may benefit future patients receiving dental implant therapy.

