### 2. Second visit: ("Implant surgery")

The second visit will be coordinated with usual and customary treatment for dental implant therapy. Prior to implant surgery, subject will be asked to complete the OHIP patient satisfaction questionnaire. This questionnaire is for research purposes only. Additionally, at the second visit, subjects will be randomized (+Graft vs. -Graft) by authorized study personnel and his/her implant, with abutment and temporary crown, will be placed (+/- Graft). The abutment and temporary crown will be placed onto the implant. If this implant is not stable, a healing abutment will be placed instead and a removable temporary will be provided within 24 hours. The experimental variable in this study is placement of a submucosal allograft in randomized patients. PerioDerm® is not an

experimental material and is available for sale and use within the USA (see Appendix A1). This visit will require approximately 2 hours.

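### Randomised subjects with a failed implant or an infected site are to be excluded, under sections that disagree, and nothing says what happens to their 12-month data or which subjects are analysed

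*Combined protocol and SAP*

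**What the plan says.** **Randomisation.** Section 6.0, Second visit: "Additionally, at the second visit, subjects will be randomized (+Graft vs. -Graft) by authorized study personnel". Integration failure and site infection can only be seen after this.

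**Failed integration.** Two sections make departure mandatory. Section 7.0 sets the trigger, "If implant integration fails or the implant site is infected, the implant will be removed or the site infection treated using standard dental therapies", and the consequence, "The subject will be excluded from this study and referred to UIC College of Dentistry for care". Section 11.2 adds: "Implant failure will result in dismissal of the subject and appropriate referral to the local dentist or UIC College of Dentistry clinics". The Fourth visit section makes it optional, saying that "the subject may be discontinued from the study", and the Fifth visit section does the same.

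**Infection.** Only Section 7.0 states an exclusion, and its wording covers a site that has been treated. Other text points the other way. The Third, Fourth and Fifth visit sections provide standard-of-care intervention for any complication, and the last two attach possible discontinuation only to failed integration. Section 7.0 itself expects that subjects with complications may need extra visits while in the study. In Section 11.2 the treating clinician "will attend to these adverse events until they have resolved and/or will refer the UIC subject to the appropriate provider as needed", and dismissal is reserved for implant failure.

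**Data and analysis.** The primary outcome is ridge volume at 12 months, from the scan at the Sixth visit; implant survival is a secondary outcome (Section 6.0, Study Outcomes). Section 9.0 names analysts and software. Section 12.0 covers sample size only. Section 5.0 allows enrolment above 40 for screening failures, not for later losses.

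**The concern.** A randomised comparison is protected only while the subjects analysed are the subjects randomised. Failed integration and infection arise after the graft is placed or withheld, and either could plausibly go with a worse ridge at 12 months. If such subjects leave and their 12-month scan is never taken, the two arms are compared among those who did well enough to stay.

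The protocol gives some reason to think that the trigger could differ by arm: its listed risks of the "allograft include local or systemic infection, dehiscence" and other events. But infection is also a listed risk of implant therapy in both arms. Section 2.0 says that the allograft is not associated with more implant failure or complications, while noting that the systematic review it cites contained no allogeneic studies. So an imbalance is neither established nor ruled out.

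Implant survival is exposed too. Failures found at the Fourth or Fifth visit are observed and can be counted, but the 12-month status of an infected subject who is excluded with the implant in place would be unknown, and the plan does not say who is in the denominator.

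**Working it through.** **What is kept for an excluded subject.** The screening scan, the pre-surgery OHIP and, for failures found at the Fourth or Fifth visit, normally the 8-week scan. No section provides for the 12-month scan, 12-month OHIP or 12-month implant status. The 8-week scan is not a substitute for the endpoint, since Section 2.0 describes resorption continuing through the first year.

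**Inputs.** From Section 12.0: 20 subjects per arm. The plan gives no exclusion rate, no SD for ridge volume and no named test, so there is no figure of its own to reproduce here. Exclusion rates and shortfalls below are assumptions, and bias is in SD units.

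**Bias.** Let a proportion *p* of an arm be excluded, and let those subjects average *k* SD lower at 12 months than the rest. The mean of all randomised subjects is then the mean of the retained subjects minus *p* × *k*, so the retained mean is too high by *p* × *k*. Hence

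bias = p_graft × k_graft − p_control × k_control.

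For 20% v 5% with *k* = 1: 0.20 − 0.05 = +0.15 SD. For 10% v 10%: 0.10 − 0.10 = 0.

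**False-positive rate.** Simulation with 100,000 runs per row: 20 randomised per arm, independent exclusion, normal outcome with SD 1 in retained subjects, no true difference across all randomised subjects, and a pooled two-sided 5% t-test on retained subjects.

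| Excluded, graft v control | Shortfall | Bias (SD; + favours graft) | False-positive rate |
|---|---|---|---|
| 10% v 10% | 1 SD | 0 | 5.0% |
| 10% v 5% | 1 SD | +0.05 | 5.2% |
| 15% v 5% | 1 SD | +0.10 | 5.9% |
| 20% v 5% | 1 SD | +0.15 | 7.2% |
| 5% v 10% | 1 SD | −0.05 | 5.3% |
| 5% v 15% | 1 SD | −0.10 | 6.0% |
| 5% v 20% | 1 SD | −0.15 | 7.1% |
| 20% v 5% | 0.5 SD | +0.075 | 5.5% |
| 20% v 5% | 2 SD | +0.30 | 13.7% |

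The mirrored rows differ only by simulation error: near 5% it is √(0.05 × 0.95 / 100,000) = 0.07 percentage points per row.

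**Precision.** With 16 v 19 analysed, the standard error relative to 20 v 20 is √(1/16 + 1/19) / √(1/20 + 1/20) = 1.073, about 7% larger.

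**Survival, assumed example.** Take 20 implants in an arm, 1 failure seen at the Fourth or Fifth visit, and 2 infected subjects excluded with the implant retained. True 12-month survival lies between 17/20 = 85% and 19/20 = 95%. Dropping the two unknowns gives 17/18 = 94.4% (exact 95% CI 72.7% to 99.9%). Counting only subjects still in the study gives 17/17 = 100%. The plan does not say which of these would be reported.

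**The case against.** *The protocol never says that these subjects are left out of the primary analysis.* This stands. A reader might infer a planned completers-only comparison, but no section states one, and the visit sections leave discontinuation for failed integration optional. The restriction is a probable consequence: an excluded subject has no planned 12-month scan, and there is no rule for missing data.

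*Exclusion of a treated infection rests on one sentence in a risk section.* This also stands. A reader might take it as settled that every infected subject leaves. The visit sections, the extra-visit sentence in Section 7.0 and the adverse-event text in Section 11.2 suggest that such subjects could stay. That is a reason to reconcile the text, because whoever applies Section 7.0 literally will lose the data.

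*The effect is small and the inputs are assumed.* Largely right. Most scenarios move the false-positive rate by one or two percentage points at most, and the largest figure needs both a fourfold imbalance and a 2 SD shortfall.

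*Survival is mostly covered.* Early failures are observed when they happen, so the gap is limited to excluded subjects who keep their implant and to the unstated denominator.

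*Volume at an empty or re-treated site is a different quantity.* Fair. Section 11.2 notes that "Following 8 weeks of healing of the site, an implant can be replaced", and the objective in Section 3.0 concerns an implant with a crown. More than one estimand can be defended, but the choice has to be made in advance.

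**Conclusion.** The point holds as a conflict and an omission. The sections differ on whether failed integration ends participation; exclusion for infection appears once and is in tension with other text; and nothing covers an excluded subject's 12-month data, the analysis set or the survival denominator. Confidence in that is high.

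It does not extend to a demonstrated bias. A reader might infer that the exclusion favours the graft, because infection is among the graft's listed risks. The documents do not support that: infection is listed for both arms, no rates are given, and the sign reverses if control loses more poor sites. With equal exclusion rates and equal shortfalls the bias is zero. Under the assumed rates (5% to 20% excluded, shortfall 0.5 to 1 SD) it is at most 0.15 SD, with a false-positive rate of 5% to about 7%; about 14% needs a 2 SD shortfall at 20% v 5%.

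This should be fixed, though it does not undermine the design. The reason to act early is that a 12-month scan not taken cannot be recovered.

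**What to change.** Reconcile the Third, Fourth and Fifth visit sections with Sections 7.0 and 11.2 on what follows failed integration and site infection. The clinical management is for the investigators to decide. Then add one data rule:

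1. Referral or the end of study treatment does not end outcome follow-up. Affected subjects who remain willing are asked for the 12-month light-based scan and OHIP, and their implant status is recorded.
2. All randomised subjects are analysed in their assigned arm. How empty or re-treated sites enter the primary analysis is fixed before the first 12-month scan; the choice of estimand is the sponsor's.
3. Every failure counts in implant survival. The denominator is all randomised subjects who received an implant, with unknown status shown separately.
4. Failures, site infections and missing 12-month scans are reported by arm.

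**Cost.** Protocol wording, and a scan and questionnaire for a few subjects: at the assumed 5% to 20%, 1 to 4 of 20 per arm. For them the 12-month visit may become research-only, which Section 6.0 aims to avoid, and some may have been referred to an outside dentist. Scans of empty or re-treated sites will add some noise.
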